Subjects must freely volunteer to participate. No coercion, implicit or otherwise, is permitted. Describe how potential subjects will be identified and approached (e.g., in class, door to door solicitation, through an ad, etc.). If the contact will be made in person, provide the statement that will be made orally to the potential subject(s). If the contact will be made in writing, submit a copy of the written communication text with this application.

Approximately **240** potential participants will be recruited at Clark University **and at other universities in the larger Worcester community** via flyering around campus as well as around Worcester in off campus public locations, email announcements, in-class announcements, **electronic advertisement boards** and via the Clark psychology subject pool. We would also like to post the contents of the flyers on a Facebook page created for the LEAF lab **as well as [name] website hosted by Clark. In order to extend recruitment beyond Clark, we will attempt to contact officials at other local universities to determine whether they will allow recruitment on their campuses and will follow their guidelines regarding local IRB approval, posting flyers on campus, email blasts, postings on electronic advertisement boards. Upon approval on other campuses, we would use all of the aforementioned resources (flyers on campus, emails, etc.) as appropriate.**

Interested students will be screened for eligibility **either in person or over the phone** (See Appendix C). If eligible, they will be schedule for an appointment, consented, asked to complete a series of questionnaires **and 2 computer tasks**, and then randomly assigned to **1 of 4 groups**.

There is no deceit involved in the study.

3. Testing Procedure:

Outline the testing procedure in sufficient detail to permit the Committee's assessment of potential psychological or physical implications (e.g. length of experiment, possible deception, physical or psychological discomfort). Attach a copy of any questionnaire or written test to be used in the study. For interviews, provide a copy of the interview questions to be used. Some research may be exempted, upon

review, from the IRB. A list of possible exempted research is available on this web page link. If you state that "minimal risk" may occur, please explain why (i.e. subject matter covered, the way responses are gathered, etc.)

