In brief, both the Picture This! and the Picture This! Plus Social Sharing groups groups will be asked to utilize their Smartphones to take photographs on a daily basis for 21 days. The participants in the Picture This! and Picture This! Plus Social Sharing Group are asked to notice and then photograph events/situations/people/places/cues that elicit positive emotion (i.e., joy, awe, gratitude). They are asked to take at least two photographs each day. Participants in the active Document This! control group are also asked to take at least two photographs each day for 21 days that they feel is a good representation of their daily lives. The passive control group is not asked to take any pictures over the 21 day period. Each day, participants in the active conditions are asked to upload the photographs taken that day to a Google Drive accessed only by study staff. Participants will not have access to other participants' photographs, only their own. Participants will be informed in the consent form that submission of photographs poses a risk to confidentiality because the photos may include "self-shots" (photos they have taken of themselves) or photos of other things that could be linked back to them personally if by chance the trained and ethically-bound research assistants happen to know the participants.

At the conclusion of the study, participants will be asked in a separate Photo Release Form if they would provide permission to study personnel to use their photographs in research manuscripts, grant proposals, educational presentations, and other media presentations (see Appendix E).

All 4 groups are asked to provide an active email address and instructed to complete a short series of questions nightly that will be emailed to them from our lab email Gmail address. The email will include a link to a survey powered by Google Docs, which includes the MDES, modified to ask participants about feelings experienced during the past 24 hours (see above for description), and 6-9 additional questions designed specifically for this study (see Appendix D for questionnaires designed for both the active and control groups). The 3 active condition groups are also asked to complete a nightly savoring exercise and to answer several questions about the exercise via a link to the exercise sent to their email (see Appendix D).

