Participants in all 3 active control groups will also be given the opportunity to choose whether they would like to be reminded to take photographs via text message or email. The text messages will be generated from the study Gmail account. Participants are reminded in the consent form that they are responsible for any charges accrued for receiving text messages if they choose that option.

At the end of each 7 day period, participants in the active **Picture This! Plus Social Sharing Group** are asked to share their photographs with a friend, relative, or loved one of their choice. Email reminders to complete the sharing exercise will be provided. The sharing should be done in person, rather than via email or over the phone. The participant may choose with whom to share the pictures and may decide to show the same person his/her pictures each week for the 3 week period or may decide to share with different people each week or some combination thereof. Scripts are provided to guide the participants (see Appendix B). Given that the participants may have taken many more than the required photographs during the prior week for this project, the time it takes to share them will vary. However, participants will be asked to limit the interaction to approximately 15 minutes. Participants in the Picture This! group and the Document This! control group are not asked to share their photographs. Following the sharing activity, participants in the Picture This! Plus Social Sharing Group are asked to answer 5 questions online, again following a link they will have received by email (see Appendix E). To keep payment equal, all other participants are also asked to complete a weekly survey of 5 questions about taking and sharing photographs.

At the completion of the 3rd 7 day period, all participants will be invited back into the laboratory to complete an exit questionnaire packet and to repeat the 2 computerized tasks they completed at baseline. This packet will include the following measures:

- 1) Demographics and Psychiatric History Follow-up
- 2) Modified Differential Emotion Scale (MDES)
- 3) Self-Other Four Immeasurables Scale
- 4) Ambiguous Situation (with 10 novel statements)
- 5) Santa Clara Brief Compassion Scale
- 6) Gratitude Questionnaire (GQ-6)
- 7) Cognitive Style Questionnaire Short Form (CSSF)
- 8) Beck Depression Inventory – II (BDI-II)
- 9) State-Trait Anxiety Inventory (STAI)
- 10) Savoring Beliefs Inventory (SBI)

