- 11) Carolina Empirically Derived Mindfulness Inventory (CEDMI)
- 12) Brief Satisfaction with Life Scale (BSWLS)
- 13) Rosenberg Self Esteem
- 14) Scale of Physical Symptoms
- 15) Pittsburgh Sleep Quality Inventory (PSQI)

- 16) Social Connectedness Scale (SCS)
- 17) MOS Social Support Scale (MOS)
- 18) Perceived Stress Scale (PSS)
- 19) Life Events Scale (LES) Respondents will be asked to consider the time that has elapsed since baseline (which should be approximately 4-5 weeks).
- 20) Emotion Regulation Questionnaire (ERQ)
- 21) TOSCA-3 with 16 novel scenarios
- 22) Irritability Question
- 23) Intervention Assessment – 5 questions created by the project staff to assess participant satisfaction with prescribed exercises and to elicit suggestions for improvement.

The following compensation/incentive schedule for completing questionnaires and participating in the study will be utilized:

- Participants who complete the baseline questionnaire packet and computer tasks will be compensated \$10 or be provided with class credit via the psychology subject pool.
- Participants who complete the exit questionnaire packet and computer tasks will be compensated \$19 or be provided with class credit via the psychology subject pool.
- Participants will be compensated \$1/day for completing the nightly online questions for a potential total of \$21.
- Participants will be compensated \$1/each weekly survey completed for a potential total of \$3.

Hypothesized Outcomes

H1: Participants in the Picture This! (PT) and Picture This! Plus Social Sharing (PTPSS) conditions will evidence increased well-being as indexed by measures of: a) depressive symptoms, b) positive affect, c) savoring beliefs, d) mindfulness e) life satisfaction, f) self esteem, g) gratitude, h) physical health and sleep quality, and i) perceived social support, relative to participants in the active control and no picture control conditions.

H2: Participants in the Pictures This! Plus Social Sharing will demonstrate greater improvement in perception of social support than those in any other condition.

Mediators of Change.

H3: Participants in the PT and PTPSS conditions will show significant changes in automatic cognitive processes including attentional biases, interpretational biases, and cognitive style assessed via behavioral tasks and self report.

H4: Changes in the aforementioned cognitive processes will account for the positive changes in mental and physical health.

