H5: Participants in the PS and PTPSS conditions will demonstrate significant changes in behavioral indicators of attentional shifts. We anticipate participants in the active experimental conditions will a) take increasingly more photographs over the course of the intervention and b) will include more social behavior as the focal point.

Supplementary Analyses

H6, exploratory: In order to inform future implementation and potential mechanisms of change, we will examine photographic content. We also anticipate changes in the quality of the photographs over the course of the intervention for the participants in both active experimental conditions. It is possible that the photographic content would be judged by independent raters to be increasingly positive over the course of the intervention. Alternatively, it is plausible that as the participant's ability to attune to the positive cues in the environment

develops, the capacity to find joy in even the most mundane objects/moments will be evident in photographs judged by independent raters to have less objectively rated positive appeal.

H7: Depressive symptoms will moderate the associations between intervention participation and daily positive affect, life satisfaction, and perceived social support, such that participants with higher levels of pre-intervention symptoms will show larger improvements in outcomes in the intervention conditions.

H5b and H6 are straightforward between-groups analyses, for which we will use ANOVA to test for significant differences between groups on the outcomes of interest. H1-H3 and H5a will be tested using mixed-factor ANOVA, with condition as a between-subjects factor and the within-subjects factor being pre-intervention measure of the outcome of interest included as predictors of the post-intervention outcome (e.g., perceived social support). Planned contrasts will probe for significant differences in effects between the experimental conditions and each control condition, as appropriate. H7 will be tested using two additional predictors, the main effect of the individual difference of interest (e.g., depressive symptoms) as well as the interaction between the individual difference and condition. H4 (mediation) will be tested using the most up-to-date evidence for bootstrapping estimates (see Hayes; Preacher & Hayes, 2008).

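### H4 is a causal claim tested only by a bootstrap, so a shared cause of mediator and outcome can support it without mediation

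*Combined protocol and SAP*

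**What the plan says.** Under Mediators of Change, H3 names the mediators: "automatic cognitive processes including attentional biases, interpretational biases, and cognitive style assessed via behavioral tasks and self report". H4 then says: "Changes in the aforementioned cognitive processes will account for the positive changes in mental and physical health".

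The analysis paragraph at the end of Supplementary Analyses gives H4 one sentence: "H4 (mediation) will be tested using the most up-to-date evidence for bootstrapping estimates", with a pointer to methodological references. For H1-H3 and H5a the same paragraph enters the "pre-intervention measure of the outcome of interest included as predictors of the post-intervention outcome". On contrasts it says: "Planned contrasts will probe for significant differences in effects between the experimental conditions and each control condition". For H4 it states no covariates, no contrast, no choice between exit values and change scores, and no sensitivity analysis. H4 is not labelled exploratory, whereas H6 is.

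On timing, section 3 (Testing Procedure) asks participants at the end of the third week to "complete an exit questionnaire packet and to repeat the 2 computerized tasks they completed at baseline". The exit packet holds the Ambiguous Situation task and the cognitive style questionnaire together with the depression, affect, sleep, symptom and support measures. The nightly survey holds an emotion scale and "6-9 additional questions designed specifically for this study", which are in an appendix that was not available for this review.

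**The concern.** Participants are randomised to condition, not to levels of attentional bias, interpretation or cognitive style. Anything that shifts both a cognitive measure and a self-reported outcome at exit makes the two correlate within arms. A mediation model reads that correlation as an effect of the mediator on the outcome. A bootstrap interval deals with sampling error in the indirect effect and does nothing about this bias. Measuring both at one visit also leaves their order in time open. An earlier mediator measure would help with order, but would not by itself remove a lasting shared cause.

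The mechanism claim is at stake. H1 and H3 predict that treatment moves both outcomes and mediators. If it does, the plan could be followed exactly and still report that cognitive change accounts for the health benefit when it does not.

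**Working it through.** The documents give no power, effect size, SD or correlation for H4, so there is no figure to reproduce. The check is a simulation of the mechanism.

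**Inputs.** Section 2 (Identification of Subjects) gives approximately 240 "potential participants will be recruited at Clark University". With four groups, and equal allocation assumed, 240/4 = 60 per group. Both experimental groups against one control is 120 v 60; one against one is 60 v 60. The rest is assumed: complete data, one mediator at a time, and a 95% percentile bootstrap with 1,000 resamples (the plan does not state the interval type). There were 4,000 trials per cell, with simulation error of at most 0.8 points.

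**Step 1: size of the spurious effect.** Let M = a·condition + e1 and Y = 0.3·condition + e2, with unit-variance errors, corr(e1, e2) = ρ and no effect of M on Y. Regressing Y on condition and M gives a mediator coefficient that tends to ρ, so the indirect effect tends to a·ρ. At a = 0.4 and ρ = 0.1/0.2/0.3 that is 0.04/0.08/0.12, or 13/27/40% of a total effect of 0.3, all of it spurious.

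**Step 2: how often the interval excludes zero with no mediation.**

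| Mediator moved by | Groups | ρ=0 | 0.1 | 0.2 | 0.3 |
|---|---|---|---|---|---|
| 0.4 SD | 120 v 60 | 3% | 18% | 53% | 69% |
| 0.4 SD | 60 v 60 | 3% | 10% | 32% | 54% |
| 0.4 SD | 96 v 48 (80% complete) | 3% | 12% | 38% | 59% |
| 0.2 SD | 120 v 60 | 1% | 5% | 17% | 24% |
| 0.2 SD | 60 v 60 | 1% | 3% | 10% | 18% |

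With a = 0 the rate is at most 5%, so the condition that treatment moves the mediator is essential.

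**Step 3: exit values, change scores or baseline covariates.** Add baselines with corr(M0, Y0) = 0.3 and stability s. The within-arm mediator-outcome correlation is then
- exit values: 0.3s² + (1 − s²)ρ
- change scores: [0.3(1 − s) + (1 + s)ρ]/2
- adjusted for both baselines: ρ

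At s = 0.5 the first two are both 0.075 + 0.75ρ. At s = 0.8 and ρ = 0 they are 0.192 and 0.03. Simulated false rates at ρ = 0 (120 v 60, 0.4 SD), in the order exit/change/adjusted, are about 12/12/4% at s = 0.5 and 53/8/7% at s = 0.8. The s = 0.8 figures use a Monte Carlo interval; a second run gave 49/7/4%. The ranking therefore depends on stability, which the documents do not give. At s = 0.5 and ρ = 0/0.1/0.2/0.3, exit values give 12/34/60/70% and adjustment gives 4/20/61/80%. Adjustment helps at low ρ and gives more false effects at 0.3. None of the three removes a shared cause that arises by exit.

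**Step 4: can the test separate the two cases?** With baseline adjustment, a real mediator effect of 0.3 and ρ = 0 gives an indirect effect of 0.4 × 0.3 = 0.12. No mediator effect and ρ = 0.3 also gives 0.4 × 0.3 = 0.12. The interval excludes zero in 81% and 80% of trials respectively (120 v 60).

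**Step 5: what a sensitivity analysis shows.** Given condition and baselines, let sY and sM be the residual SDs and p the residual correlation. At an assumed correlation r the indirect effect is â·(sY/sM)·[p − r·√((1 − p²)/(1 − r²))]. Share of trials with the lower limit above zero at r = 0.1/0.2/0.3:

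| Truth | 120 v 60 | 60 v 60 |
|---|---|---|
| No mediation, ρ = 0.3 | 63/23/2% | 41/15/2% |
| Real effect 0.3, ρ = 0 | 59/19/2% | 37/11/1% |

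The rows are nearly the same. The analysis measures how fragile a result is; it does not tell real from spurious mediation. A mediator path just significant at 0.05 is brought to zero by a residual correlation of t/√(t² + df) with df = n − 5, which is 0.15 at n = 180 and 0.18 at n = 120.

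**The case against.** The strongest reply is that this affects any mediation analysis in which only treatment is randomised, that no figure in the documents is contradicted, and that every rate rests on assumed inputs. That is true, and it limits what the percentages mean: they show the mechanism and do not predict this trial's result. The correlation may also differ by mediator; a letter-response task may share less with self-reported outcomes than a questionnaire does. But the argument needs only a moved mediator, which H3 predicts, and a modest shared cause.

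Four stronger readings are tempting and should not be drawn.

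- A reader might infer that the plan leaves baseline out of H4. The paragraph is silent. H4 speaks of changes, which may mean change scores, and it defers to references not available here.
- A reader might infer that baseline adjustment is the remedy. Step 3 shows otherwise. Under a different simulated shared cause, a stable trait explaining 30% of variance (120 v 120, mediator moved 0.3 to 0.5 SD), change scores gave 4-7% false effects and adjustment gave 23-27%.
- A reader might infer that nothing relevant is measured between baseline and exit. The nightly questions cannot be seen, and H5 treats the daily photographs as behavioural signs of attention. However, H4 refers back to the H3 processes, and the passive control group takes no study photographs.
- A reader might infer that the proposed sensitivity analysis tests mediation. Step 5 shows that it does not.

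**Conclusion.** The concern holds. H4 is worded causally and its only stated test can be passed without mediation. With the mediator moved 0.4 SD at 120 v 60, no true mediator effect and no baseline in the model, that happens in about 18/53/69% of trials at residual correlations of 0.1/0.2/0.3. It falls to about 5/17/24% at 0.2 SD and to at most 5% if the mediator is not moved. Group sizes, effect sizes, correlations, interval type and complete data are assumptions. The structural point does not depend on them: randomisation leaves the mediator-to-outcome path unprotected, and a bootstrap does not repair it. The randomised comparisons under H1 and H2 are not affected.

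**What to change.** In the analysis paragraph under Supplementary Analyses:

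1. Beside each indirect effect, report the residual mediator-outcome correlation that would reduce it to zero, and the interval recomputed at correlations fixed in advance (for example 0.1, 0.2 and 0.3). Describe this as a measure of fragility that does not distinguish real from spurious mediation.
2. Limit the H4 conclusion to: 'consistent with mediation; direction and absence of confounding not established'.
3. As a secondary step, state the H4 model and include baseline mediator and baseline outcome as covariates. Note that this removes confounding by those baseline values only and can raise the rate of false indirect effects at larger residual correlations.

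The cost is plan text and one extra analysis of data already due to be collected, with no new measurement. The real price is a weaker claim about mechanism. Even a true mediator effect of 0.3 will often not survive: at an assumed correlation of 0.3 the interval stays above zero in only about 2% of trials (120 v 60) or 1% (60 v 60).

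### H6 accepts either a rise or a fall in rated photograph positivity and names a test with no time factor, so no directional result can count against the mechanism and declining effort is not separated from attunement

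*Combined protocol and SAP*

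**What the plan says.** Under Supplementary Analyses the plan introduces the hypothesis as follows: "H6, exploratory: In order to inform future implementation and potential mechanisms of change, we will examine photographic content". The prediction has no sign: "We also anticipate changes in the quality of the photographs over the course of the intervention for the participants in both active experimental conditions".

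Two opposite outcomes are then offered.

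- Rising ratings: "It is possible that the photographic content would be judged by independent raters to be increasingly positive over the course of the intervention". No mechanism is named in that sentence.
- Falling ratings, introduced by "Alternatively, it is plausible that as the participant's ability to attune to the positive cues in the environment" and ending with photographs that have less rated appeal ("will be evident in photographs judged by independent raters to have less objectively rated positive appeal"). Here the fall is explicitly attributed to growing attunement.

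The analysis paragraph that closes the same section says: "H5b and H6 are straightforward between-groups analyses, for which we will use ANOVA to test for significant differences between groups on the outcomes of interest".

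Three other places bear on the point.

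- Section 3 (Testing Procedure) gives Document This! the same minimum quota as the experimental arms: two photographs a day for 21 days. The passive control takes none, so at most three arms supply study photographs.
- Section 3 also sends all four groups a nightly MDES, "modified to ask participants about feelings experienced during the past 24 hours".
- H5a predicts that the number of photographs will grow in the experimental arms. The final paragraph plans exploratory growth curves and mentions that photograph positivity may go up.

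**The concern.** A hypothesis meant to inform mechanism should say which result would speak for the mechanism and which against it. H6 accommodates both signs of change and gives no rule for choosing between them.

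The falling outcome is the difficult one. A fixed daily quota over three weeks could produce less appealing photographs simply because novelty runs out or effort drops. The plan does not name that rival, and rated appeal alone cannot separate it from a participant who now takes pleasure in ordinary things.

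The named test adds a second gap. H6 is about change over the intervention, but a between-groups ANOVA without time or a change score compares levels. The experimental arms photograph things that bring joy or peace, and Document This! photographs representative daily life. Mean ratings could differ for that reason alone, with no change in anyone.

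At stake is the interpretation of one exploratory mechanism analysis and what it passes on to later implementation work.

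**Working it through.** **No figure to reproduce.** The plan gives no alpha, power, effect size or SD for H6. The textual check comes first, then an illustration on stated assumptions.

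**What each result would mean under H6 as worded**

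| Result in PT/PTPSS | Fit with H6 |
|---|---|
| Ratings rise | Allowed by the first outcome |
| Ratings fall | Allowed by the second outcome, attributed to attunement |
| No change, or no difference from Document This! | Does not support H6 |

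The first two rows are the directional gap. The third shows that H6 can still fail to be supported.

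**How often could declining effort give a significant fall against Document This!?**

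Inputs from the plan: about 240 recruits, 4 groups, and at least 2 photographs a day for 21 days, so 2 × 21 = 42 per person.

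Assumptions:
- equal allocation, so 60 per arm, giving 120 in PT + PTPSS and 60 in Document This!;
- all 42 photographs rated and spread evenly over the period;
- photo-level residual SD of 1, and between-person slope SD of 0.3 to 0.5 (slope = change over the whole 21 days);
- two-sided alpha of 0.05;
- no fatigue at all in Document This!.

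With time scaled from 0 to 1, evenly spread photographs have time variance 1/12. The sampling variance of one person's slope is then 1/(42/12) = 1/3.5 = 0.286.

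SE of the difference in mean slope = sqrt[(0.286 + slope SD²) × (1/120 + 1/60)]

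- Slope SD 0.3: sqrt(0.376 × 0.025) = 0.097
- Slope SD 0.5: sqrt(0.536 × 0.025) = 0.116

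Chance of a significant fall ≈ Φ(fall/SE − 1.96):

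| True fall | Slope SD 0.3 | Slope SD 0.5 |
|---|---|---|
| 0.20 SD | Φ(2.06 − 1.96) = 0.54 | Φ(1.73 − 1.96) = 0.41 |
| 0.15 SD | Φ(1.55 − 1.96) = 0.34 | Φ(1.30 − 1.96) = 0.25 |

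If Document This! declines equally, the true difference is zero and the rejection rate is the nominal 5%.

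**Cross-check by simulation.** This used 10,000 runs of a three-arm ANOVA, 60 per arm, on each participant's change in rated positivity, in units of the SD of that change.

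- Equal fall of 0.3 SD in all three photo arms: rejects in 5.0% of runs.
- Fall in PT/PTPSS only: rejects in 37% of runs at 0.3 SD and 81% at 0.5 SD.

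The scales differ. A fall of 0.2 photo-level SD equals 0.2/sqrt(0.376) = 0.33 or 0.2/sqrt(0.536) = 0.27 SD of change. The 0.3 SD simulation is therefore the nearest comparison, and its omnibus three-arm test is somewhat less sensitive than the 120 v 60 contrast.

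Both calculations analyse change, which the H6 text does not specify. They describe a reasonable controlled reading of H6, not the ANOVA as written.

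**The case against.** The strongest reply is that the control arm deals with fatigue. Document This! has the same quota for the same 21 days, H6 is tested between groups, and shared fatigue cancels. That stands, but it needs an analysis of change, which the plan does not name, and equal decline, which is uncertain. Photographs chosen for joy may have further to fall towards ordinary scenes than photographs that already show daily life.

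A reader might infer that H6 cannot fail. The documents do not support this: it anticipates change and compares groups, so a null result would leave it unsupported.

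A reader might also infer that the plan commits to reporting fatigue as skill, or that it credits both directions to attention. Both outcomes are worded tentatively, and attunement is tied only to the fall. Misreading is a possibility the plan leaves open, not something it announces.

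An uncontrolled within-arm trend would detect a given drift more often than the figures above. That is not the named H6 test. The exploratory growth curves might be read that way, but the direction they mention is upward.

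There are existing safeguards. H5a already examines photo counts, and falling effort would tend to contradict it. Mechanism claims rest mainly on H3 and H4. Appendix D, not available here, holds further nightly questions that may bear on how participants felt about the exercise. Listing rival possibilities is also normal in exploratory work. These points limit the importance of the gap. They do not supply a reading rule or a time factor for H6.

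**Conclusion.** The concern holds as a minor point about one exploratory analysis. H6 predicts change without a sign, links the ratings to no other measure, and names a test that does not address change over time. No directional result can count against the mechanism, and a fall from declining effort in PT/PTPSS could be taken for attunement.

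The size is moderate and conditional: about 41-54% for a 0.2 SD fall and 25-34% for 0.15 SD if only the experimental arms tire, and about 5% if all photo arms tire equally. These rest on assumed variances, equal arms, full photo compliance and a slope contrast that the plan does not state. They show what drift could be detected, not that drift will occur. H1-H2 do not depend on it.

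**What to change.** 1. Replace the H6 ANOVA with a mixed model of daily rated positivity: participant random effects, day × condition, and a contrast of PT/PTPSS with Document This!.
2. State before rating begins which direction, relative to Document This!, supports attunement.
3. Read a fall as consistent with attunement only if it exceeds the fall in Document This! and both same-day nightly MDES positive affect and photo counts (H5a) are stable or rising. Otherwise report it as not distinguishable from fatigue or drift.
4. State the limits. The MDES covers the whole day, not the photographs, so stable affect does not exclude boredom with the task. Document This! photographs may start with lower appeal and have less room to fall, so fatigue alone could meet the comparison. The rule supports a reading but does not prove it.

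The cost is a paragraph and some modelling. The uploads and nightly MDES are already planned. The plan does not say how many photographs will be rated; at the minimum quota the three photo arms would yield 180 × 42 = 7,560 under the 60-per-arm assumption, so the rating load should be settled in the same paragraph. The other consequence is that H6 could then be contradicted by a directional result.
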